6.8.5 Subjects Lost to Follow-up

All subjects who fail to return to the study site will be contacted by telephone to determine the reason(s) why the subject failed to return for the necessary visit or elected to discontinue from the study. If a subject/caregiver is unreachable by telephone after a minimum of three documented attempts (one attempt on three different days using at least 2 different forms of communication), a certified letter will be sent requesting that the subject contact the investigator to confirm the final status of their molluscum lesions and to return any outstanding study drug. These actions will be reported on the subject's study record and a copy of the follow-up letter maintained in the investigator's file. The certified letter should include the following questions:

- Please choose one of the following:
 - I/my child want to continue participating in this study.

- I/my child am no longer interested in participating in this study and withdraw my consent.
- At the time you chose to stop participating in study visits, was your/your child's molluscum contagiosum:
 - Resolved (no lesions left)
 - Resolving (number of lesions is decreasing)
 - Unchanged (number of lesions is similar to previous visit)
 - Worsening (number of lesions increased)

An investigator may withdraw a subject from the study when a subject is lost to follow-up.

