7.1 Efficacy Assessments

7.1.1 Molluscum Contagiosum Lesion Counts

Molluscum contagiosum is a viral infection characterized by small, discrete, waxy, skin-colored, dome-shaped raised papules, an average of 3–5 mm in diameter. The papules may be umbilicated and contain a caseous plug. When the lesions are squeezed or traumatized, a creamy, grey-white material can be extruded. If the investigator cannot clearly differentiate the lesions as is the case for agminated (clustered) lesions this should be counted as one lesion. If the investigator can differentiate and count the umbilical tops separately, each lesion should be counted separately. The investigator should be consistent with the method of recording agminated lesions throughout the study.

For the purpose of this clinical trial, only treatable MC lesions are counted. Treatable lesions are any active (raised, palpable) MC lesions that are dome-shaped, pearly, and shiny white top centered papules that are at least 2 cm away from the ocular region. In clinic, investigators may choose to palpate the lesion to confirm if it is raised. Treatable region is any skin area containing a molluscum lesion, with the exception of the periocular region.

All study personnel who will perform lesion counts must pass the study training including lesion count training. Training on how to accurately count the number of MC lesions will be provided.

Mapping of lesions: At every visit from Baseline through Week 12, all lesions should be recorded on the body map and will clearly note the location of each lesion or agminated lesion. The lesion map is intended to assist study personnel in performing lesion counting and scar/keeloid assessment. The body map will also be shared with the subjects/caregivers at Week 2 to assist with counting of lesions.

Definition of Clearance: For the purpose of this study, “clear” means resolution of the active (raised, palpable) treatable molluscum lesion(s). After a lesion has cleared, the residual surface changes such as a pitted scar (indentation), hyperpigmentation, or hypopigmentation may remain. Additional details will be provided in the lesion count training. Complete clearance can only be confirmed by an in-clinic lesion count.

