## 10.1 Efficacy Endpoints

The primary efficacy endpoint is the proportion of subjects with complete clearance of all treatable MC at Week 12.

The secondary efficacy endpoints are the following:

- 1) Proportion of subjects achieving a lesion count of 0 or 1 of all treatable MC at Week 12.
- 2) Proportion of subjects achieving at least a 90% reduction from Baseline in the number of all treatable MC at Week 12.
- 3) Proportion of subjects with complete clearance of all treatable MC at Week 8.
- 4) Percent change from Baseline in the number of all treatable MC at Week 4.

Complete clearance is defined as having a total number of lesions count of 0.

The exploratory endpoints are the following:

- Percent change from Baseline in number of treatable MC at each visit (Weeks 2, 8, 12)
- Proportion of subjects achieving a lesion count of 0 or 1 of all treatable MC at Weeks 2, 4, and 8
- Proportion of subjects achieving at least a 90% reduction from Baseline in the number of all treatable MC at Weeks 2, 4, and 8
- Proportion of subjects achieving at least a 75% reduction from Baseline in the number of all treatable MC at Weeks 2, 4, 8, and 12
- Absolute change from Baseline in number of treatable MC at Weeks 2, 4, 8, 12
- Proportion of subjects with complete clearance of all treatable MC at Week 2 and Week 4 visits
- Time to complete clearance of all treatable MC, defined as the days between the date of first dose and the first date of clearance. Subjects who do not achieve complete clearance will be censored at the date of the last lesion count assessment.
- Proportion of subjects who have a recurrence of MC after the first visit at which complete clearance was observed, defined as the total lesion count being greater than 0 at any point after achieving a count of 0
- Subject-reported spread to household members as measured by any new occurrence of MC in household members of subjects at each visit (Weeks 2, 4, 8, 12)
- Investigator Global Severity Assessment at Baseline, Week 12, and Week 24
- Subject Global Severity Assessment at Baseline, Week 12, and Week 24
- Investigator Global Impression of Change at Week 12 and Week 24

- Subject Global Impression of Change at Week 12 and Week 24

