## 10.4 Handling of Dropouts or Missing Data

In analyses based on response, a missing response will be considered a non-responder.

For a sensitivity analysis, subjects with missing lesion count at Week 12 but who demonstrated complete clearance at the last collected lesion assessment will be counted as responders.

An additional sensitivity analysis using multiple imputation will be performed to address subjects with missing lesion count at Week 12. A monotone imputation model will be utilized in the following steps:

1. The lesion count data will be imputed to follow a monotone missing data pattern using the Markov chain Monte Carlo method for 10 imputations.
2. Each of the 10 imputations will then be imputed a further 10 times using a monotone regression method to impute the remaining missing data and the Week 12 lesion count using lesion count assessments at Weeks 2, 4, and 8, treatment group, investigator type (dermatologist vs other), BOTE score at Baseline (no inflammation [BOTE=0] vs mild/moderate/severe/very severe inflammation [BOTE $\geq$ 1]), age (0 to <3, 3 to <4, 4 to <5, 5 to <6, 6 to <7, 8 to <9, 9 to <12, and  $\geq$ 12 years old), and baseline lesion count as covariates.

3. Complete Clearance at Week 12 will be re-derived based on the imputed values and then analyzed using the primary analysis model. The results of the 100 analyses will be transformed into a normal statistic and combined into a single analysis using PROC MIANALYZE.

The ROUND and MINIMUM options will be utilized in Steps 1 and 2 to ensure imputed values are non-negative integers. The seed to be used is 20200727.

For subjects with a missing lesion count at Week 12 and identified as “Lost to Follow-up” by the investigator, the following sensitivity analysis will be performed. These lost to follow-up subjects will be contacted to obtain a patient reported outcome of MC disease status at the end of their study participation of either ‘Resolved (no lesions left)’, ‘Resolving (number of lesions decreasing)’, ‘Unchanged (number of lesions similar to previous clinic visit)’, or ‘Worsening (number of lesions increased)’. A reported response endpoint will be derived in the following manner:

- If a subject has a Week 12 lesion count assessment, then the subject will be deemed a responder if the count was 0.

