- If the subject did not have a Week 12 lesion count assessment and the response to the disease status was ‘Resolved (no lesions left)’ or ‘Resolving (number of lesions decreasing)’, then the subject will be deemed a responder.
- Otherwise, the subject will be deemed a non-responder.

The sensitivity analysis of this patient reported response will be analyzed in the same manner as the primary endpoint. A list of the patient reported outcome of MC disease status will be provided.

A sensitivity analysis on the manner of assessment of lesion counts at Week 12 (in-clinic vs. remote) may be performed where subjects with only a remote assessment will be counted as non-responders.

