**TABLES, FIGURES, AND GRAPHS**

Table Number	Table Title	Analysis Population
14	TABLES, FIGURES, AND GRAPHS REFERRED TO BUT NOT INCLUDED IN THE TEXT	
14.1	DEMOGRAPHIC DATA	
14.1.1.1	Subject Disposition	Enrolled
14.1.1.2	Enrollment by Site	ITT
14.1.2.1	Demographic and Baseline Characteristics	Safety
14.1.2.2	Demographic and Baseline Characteristics	ITT
14.1.2.3	Demographic and Baseline Characteristics	PP
14.1.3.1	Study Drug Exposure	Safety
14.1.3.2	Study Drug Compliance	Safety
14.1.4	Significant and Major Protocol Deviations	ITT
14.1.5	Medical History	ITT
14.1.6.1	Prior Medications	ITT
14.1.6.2	Concomitant Medications	ITT
14.2	Efficacy data	
14.2.1.1	Complete Clearance Lesion Count Response at Week 12	ITT
14.2.1.2	Complete Clearance Lesion Count Response at Week 12	PP

Table Number	Table Title	Analysis Population
14.2.1.3	Sensitivity Analysis: Complete Clearance Lesion Count Response at Week 12	ITT
14.2.1.4	Sensitivity Analysis: Complete Clearance Lesion Count Response at Week 12	PP
14.2.1.6	Proportion of Subjects with Complete Clearance at Week 12 by Subgroup	ITT
14.2.1.7	Dropout Sensitivity Analysis: Complete Clearance Lesion Count Response at Week 12	ITT
14.2.1.8	One Subject Per Household Sensitivity Analysis: Complete Clearance Lesion Count Response at Week 12	ITT
14.2.1.9	Exploratory Analysis of the Variability of Treatment Effect of Complete Clearance Lesion Count Response at Week 12 Across Pools of at Least 18 Subjects	ITT
14.2.1.10	Exploratory Analysis of the Variability of Treatment Effect of Complete Clearance Lesion Count Response at Week 12 Across Pools of at Least 12 Subjects	ITT
14.2.1.11	Multiple Imputation Sensitivity Analysis: Complete Clearance Lesion Count Response at Week 12	ITT
14.2.1.12	Patient Reported Response Sensitivity Analysis: Complete Clearance Lesion Count Response at Week 12	ITT
14.2.2.1.1	Complete Clearance Lesion Count of 0 or 1 Response at Week 12	ITT
14.2.2.1.2	Complete Clearance Lesion Count of 0 or 1 Response at Week 12	PP
14.2.2.2.1	Summary of a 90% Reduction in Lesion Counts from Baseline Response at Week 12	ITT
14.2.2.2.2	Summary of a 90% Reduction in Lesion Counts from Baseline Response at Week 12	PP
14.2.2.3	Complete Clearance Lesion Count Response at Week 8	ITT
14.2.2.4.1	Percent Change from Baseline in Lesion Counts by Visit	ITT
14.2.3.1	Complete Clearance Lesion Count of 0 or 1 Response at Weeks 2, 4 and 8	ITT

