14.2.3.10.3	Cumulative Distribution Function Plot by Subject Global Impression of Change Improvement Category	ITT

Section 16.2: List of Data Listings

ICH Listing Number	Listing Title	Analysis Population
16.1.7	Subject Randomization	ITT
16.2	SUBJECT DATA LISTINGS	
16.2.1	Discontinued subjects	
16.2.1.1	Subject disposition	Enrolled
16.2.2	Protocol deviations	
16.2.2.1	Protocol Deviations	ITT
16.2.2.2	Inclusion/Exclusion Criteria	Enrolled
16.2.3	Subjects excluded from the efficacy analysis	
16.2.3.1	Analysis Populations	Enrolled
16.2.4	Demographic data	
16.2.4.1	Demographic and Baseline Characteristics	ITT
16.2.4.2	Patch Testing Consent/Assent	Enrolled
16.2.4.3	Medical History	ITT
16.2.4.4	Prior and Concomitant Medications	ITT
16.2.4.5	Study Exit Interview Consent/Assent	Enrolled
16.2.5	Compliance and/or drug concentration data	
16.2.5.1	Study Drug Administration	Safety
16.2.5.2	Study Drug Accountability	Safety
16.2.5.3	Dosing Plan and Treatment Modification	Safety
16.2.5.4	Treatment Compliance	Safety
16.2.6	Individual efficacy response data	
16.2.6.1	Lesion Counts	ITT
16.2.6.2	Lesion Count Derived Efficacy Variables and Time to Complete Clearance	ITT
16.2.6.3	Household Transmission	ITT
16.2.6.4	Global Severity Assessment	ITT
16.2.6.5	Global Impression of Change	ITT
16.2.6.6	Patient Reported Outcome of Molluscum Contagiosum Disease Status based on Lost to Follow-up Contact	ITT

ICH Listing Number	Listing Title	Analysis Population
16.2.7	Adverse events listings	
16.2.7.1	All Adverse Events	Safety
16.2.7.2	Adverse Events Leading to Study Discontinuation	Safety
16.2.7.3	Ongoing Treatment Related Adverse Events	Safety
16.2.7.4	Post Treatment Adverse Events	Safety
16.2.8	Listing of individual laboratory measurements by subject, when required by regulatory authorities	
16.2.8.1	Urine Pregnancy Test	Safety
16.2.9	Other data	
16.2.9.1	Beginning-of-the-End (BOTE) Inflammation Score	Safety
16.2.9.2	Local Skin Reactions (LSR)	Safety
16.2.9.3	Physical Examination	Safety
16.2.9.4	Scarring/Keloid Assessment	Safety
16.2.9.5	Patch Testing	Safety
16.2.9.6	Telephone Contact	ITT
16.2.9.7	Subjects who Require a Narrative	ITT
16.2.9.8	COVID-19 Impacted Visits	ITT

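### The patient-reported Week 12 sensitivity analysis counts subjects who say lesions remain as complete clearance; in the multiple imputation, the handling of the lower bound sets the imputed clearance rate

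*SAP*

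**What the plan says.** **Endpoint.** SAP 10.1: "Complete clearance is defined as having a total number of lesions count of 0". Protocol 10.3.1 likewise requires a lesion count of zero at Week 12. In the primary analysis, a missing response is a non-response (SAP 10.4).

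**Patient-reported analysis.** SAP 10.4 has lost-to-follow-up subjects contacted and offers four replies: Resolved, Resolving, Unchanged and Worsening. A subject with a Week 12 count is a responder only if that count is 0. A subject without one is a responder after either Resolved or Resolving: "Resolving (number of lesions decreasing)’, then the subject will be deemed a responder". The follow-up letter in protocol 6.8.5 asks about status "At the time you chose to stop participating in study visits", not at Week 12. The variable is analysed like the primary endpoint, and Table 14.2.1.12 in SAP Appendix C is titled "Patient Reported Response Sensitivity Analysis: Complete Clearance Lesion Count Response at Week 12". Listing 16.2.6.6, "Patient Reported Outcome of Molluscum Contagiosum Disease Status based on Lost to Follow-up Contact", shows the individual replies.

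**Multiple imputation.** In SAP 10.4, Step 1 makes the missing pattern monotone by Markov chain Monte Carlo. Step 2 proceeds by "using a monotone regression method to impute the remaining missing data and the Week 12 lesion count". On the bound, the text says only: "The ROUND and MINIMUM options will be utilized in Steps 1 and 2 to ensure imputed values are non-negative integers". Step 3 re-derives clearance from the imputed counts and fits the primary model.

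**The concern.** Protocol 10.3.1 allows extra sensitivity analyses so that the efficacy result does not hinge on how missing data are handled. Each such analysis should therefore change the missing-data assumption and keep the endpoint.

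The patient-reported analysis changes the endpoint. Within one variable, an observed subject with a single remaining lesion is a non-responder, while an unobserved subject with any number of decreasing lesions is a responder. A reader of Table 14.2.1.12 would take the second subject as cleared.

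The multiple imputation keeps the endpoint but reaches it indirectly. I read the regression step as linear. A linear model gives a continuous draw with no mass at zero, whereas the sample-size section plans for 20% and 29.5% zeros. Imputed zeros then arise only from rounding and from whatever is done with draws below the minimum. If the imputed rate is fixed by that mechanism, agreement with the primary analysis says little about robustness.

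**Working it through.** **Plan's own figure.** Inputs from SAP 5: 425 per arm, 20% against 29.5%, two-sided 0.05.
- Standard error under the null: √(2 × 0.2475 × 0.7525 / 425) = 0.02960.
- Standard error under the alternative: √((0.20 × 0.80 + 0.295 × 0.705) / 425) = 0.02942.
- Power = Φ((0.095 − 1.96 × 0.02960) / 0.02942) = 89.6%, which reproduces the stated 90%. Neither analysis discussed here enters this calculation.

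**Resolving replies: the texts side by side.**

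| Reply, no Week 12 count | Lesions left when visits stopped? | Meets count of 0? | SAP 10.4 rule |
|---|---|---|---|
| Resolved | No (self-report) | Yes, at that time | Responder |
| Resolving | Yes | No | Responder |
| Unchanged or Worsening | Not stated to be zero | No | Non-responder |

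The Resolving row is the contradiction. It needs no assumption.

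**Resolving replies: size.**
- One reply: 1/425 = 0.24 point in its arm.
- Missing per arm (assumed): the study discontinuation rates of 15.3% and 17.2% in protocol 2.1 give 425 × 0.153 = 65.0 and 425 × 0.172 = 73.1. These rates are not dated to Week 12. SAP 7 also maps early-termination counts on Days 72 to 98 to Week 12, so the true number may be lower.
- Assumed: 10% of the missing are lost to follow-up and reply, and 30-60% of those say Resolving.
- Low: 65.0 × 0.10 × 0.30 = 1.95 subjects; 1.95/425 = 0.5 point.
- High: 73.1 × 0.10 × 0.60 = 4.39 subjects; 4.39/425 = 1.0 point.
- The figure is proportional to the reply share: twice the replies, twice the points.
- Arm difference: equal Resolving shares, with equal missingness and reply rates, leave it unchanged. At 60% in one arm and 30% in the other it moves by 65.0 × 0.10 × 0.30 / 425 = 0.46 to 73.1 × 0.10 × 0.30 / 425 = 0.52 point, in either direction.

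**Imputation: chance that a draw becomes 0.** Let m be the predicted Week 12 count and s the residual SD. Both are assumed (m from 0 to 12, s from 6 to 18), because the documents give neither.
- Redrawn until non-negative, then rounded: [Φ((0.5 − m)/s) − Φ(−m/s)] / [1 − Φ(−m/s)].
- Rounded, then redrawn if negative: [Φ((0.5 − m)/s) − Φ((−0.5 − m)/s)] / [1 − Φ((−0.5 − m)/s)].
- Negative draws set to 0: Φ((0.5 − m)/s).

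| m | s | Redrawn | Rounded, then redrawn | Set to 0 |
|---|---|---|---|---|
| 0 | 6 | 6.6% | 12.5% | 53% |
| 0 | 18 | 2.2% | 4.3% | 51% |
| 12 | 6 | 0.5% | 0.9% | 2.8% |
| 12 | 18 | 1.2% | 2.3% | 26% |

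With 65 to 73 missing per arm, redrawing adds between 65.0 × 0.005 / 425 = 0.08 and 73.1 × 0.066 / 425 = 1.1 points to an arm's rate. That is close to the non-responder rule. Setting to 0 adds between 65.0 × 0.028 / 425 = 0.4 and 73.1 × 0.53 / 425 = 9.1 points. These extremes assume one m and s for all missing subjects.

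**The case against.** **These analyses are only supportive.** This stands. The primary rule is non-response for missing data. The last-observed-clearance analysis, the per-protocol analysis and the 14 dropout scenarios in SAP 11.1 stress it independently.

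**The first point is only a label.** SAP 10.4 calls the variable a reported response, and the table title also says that it is patient-reported. In part this stands: calling it improvement would be coherent. But the table still says complete clearance, nothing in SAP 10.4 presents the rule as a deliberately generous scenario, and Resolved is already a separate reply that gives a coherent one. The listing shows the replies but does not change the modelled estimate.

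**Few subjects will reply.** Protocol 6.8.5 sends the letter only after at least three failed contact attempts, so the number may be small. This stands, and the contradiction does not depend on the number.

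**The multiple imputation does analyse clearance.** This stands. A reader might infer that it ignores clearance, but Step 3 re-derives it, and imputing a count first is not an error in itself. Whether bias follows depends on software behaviour that the documents do not state. The redraw case lands near the primary rule.

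**Protocol 7.1.1 could seem to settle the matter**, since "Complete clearance can only be confirmed by an in-clinic lesion count". It cannot carry the argument, because it would rule out Resolved replies as well.

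**Conclusion.** The Resolving rule is wrong as written: it contradicts the definition of the endpoint that the table claims to show. Its size is 0.24 point per reply. The range of 0.5-1.0 point per arm rests on an assumed 10% reply share, an assumed 30-60% Resolving share, and discontinuation rates borrowed from the two earlier phase 3 studies.

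The imputation point is a weakness and a cheap improvement, not a demonstrated bias. Under the assumed values, the chance of an imputed 0 is 0.5-6.6% with redrawing and 2.8-53% with setting to 0, and the SAP does not say which applies. It also rests on reading the regression as linear.

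A reader might infer that the plan inflates the primary result or tilts it towards SB206. The documents do not support that. Neither analysis enters the primary test, the fixed-sequence error control or the power. Resolving replies can fall in either arm, and nothing in the documents says that they would favour one.

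**What to change.** **Main change.** In SAP 10.4, count only the Resolved reply as response for subjects without a Week 12 count. State that this is self-reported and not dated to Week 12. Show Resolving replies by arm on a separate descriptive line of Table 14.2.1.12. This costs a few words of SAP text and one table line.

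**Secondary change.** In Step 2, impute Week 12 clearance as 0/1 by monotone logistic regression, or impute the counts by predictive mean matching, with the same covariates. This costs a few more lines of imputation code.

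Both changes should be made before unblinding. Neither needs new data.

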## 10.5 Interim Analysis and Data Monitoring

When approximately 200 subjects are randomized, a DSMB will review all available unblinded safety data (including patch testing). All responsibilities of the DSMB and details of the analysis and data to be reviewed is detailed in the DSMB charter.

## 10.6 Examination of Subgroups

Subgroup analyses of complete clearance at Week 12 for investigator type (dermatologist vs other), household number of randomized subjects (1 subject per household vs 2 subjects per household), and BOTE score at Baseline (no inflammation [BOTE=0] vs mild/moderate/severe/very severe inflammation [BOTE≥1]) will be presented in a forest plot for the ITT Population. An additional subgroup analysis of complete clearance at Week 12 for age

(<1 year old,  $\geq 1$  to <2 years old,  $\geq 2$  to <6 years old,  $\geq 6$  to <12 years old,  $\geq 12$  to <18 years old,  $\geq 18$  years old) and onset of MC symptoms duration prior to baseline ( $\leq 6$  months vs  $>6$  months) will be summarized descriptively for the ITT Population.

### 10.7 Multiple Comparison/Multiplicity

The familywise error rate with respect to the primary endpoint and secondary endpoints will be strongly controlled at the  $\alpha=0.05$  level using a hierarchical fixed sequence method testing strategy in the order listed in Section 10.1. If the primary endpoint is not statistically significant at the  $\alpha=0.05$  level, the secondary efficacy endpoints will be considered not significant. If the primary endpoint is statistically significant at the  $\alpha=0.05$  level, then the secondary efficacy endpoints will be tested in the following hierarchical fixed sequence:

- 1) Proportion of subjects achieving a lesion count of 0 or 1 of all treatable MC at Week 12.
- 2) Proportion of subjects achieving at least a 90% reduction from Baseline in the number of all treatable MC at Week 12.
- 3) Proportion of subjects with complete clearance of all treatable MC at Week 8.
- 4) Percent change from Baseline in the number of all treatable MC at Week 4.

At each subsequent test of the secondary efficacy endpoints, if the secondary efficacy endpoint is not statistically significant at the  $\alpha=0.05$  level, the remaining secondary efficacy endpoints will be considered not statistically significant. If the secondary endpoint is statistically significant at the  $\alpha=0.05$  level, then the next subsequent secondary efficacy endpoint will be tested following the sequence.

